## 9.5 Reporting and Exclusions

### 9.5.1 Evaluation of Toxicity

All patients will be evaluable for toxicity from the time of their first treatment with cobimetinib, atezolizumab, and CDX-1127 (varlilumab). A baseline measurement and at least 1 laboratory or other safety-related measurement obtained after at least 1 dose of study treatment may be required for inclusion in the analysis of a specific safety parameter (e.g., lab shifts from baseline). A complete list of all AE data will be provided along with an assessment of NCI CTCAE grade and relationship to study drug. The incidence of AEs will be tabulated by subgroups of interest (e.g. grade 3 or higher, organ class, relationship to study drug). For analyses at the individual level, the highest grade and relationship to study drug will be assumed if multiple events have occurred. Toxicity will be tabulated by type and grade and will be summarized with descriptive statistics. Other safety data will be assessed in terms of physical examination, clinical chemistry, hematology, vital signs, and ECGs. Negative binomial regression and Cox proportional hazards models will be used to assess the rate of AE and time to first toxicity, respectively.

While the combination of our proposed three study medications (or similar in-class alternatives) have not been studied in human trials, CDX-1127 (varlilumab) has been shown to be well tolerated in combination with anti-PD1, Nivolumab in patients with advanced solid tumors (NCT02335918). Additionally, the combination of cobimetinib and atezolizumab demonstrated a favorable safety profile at full doses in BTC patients (CTEP 10476). The present study will be continuously monitored for adverse events.

We will incorporate the following safety run-in and stopping rule that will be applied within each treatment group, A and B, respectively: if 2 or more “unacceptable toxicities,” at least possibly attributable to study therapy, are observed among the first 6 patients enrolled in the same treatment arm during their initial treatment cycle, we will pause the accrual in that arm and re-

evaluate safety. Accrual will be limited until the safety has been achieved in the first 6 patients in each arm, respectively.

“Unacceptable toxicities” are defined as the following treatment-related events:

- Any grade  $\geq 2$  uveitis, retinitis, eye pain, or blurred vision that does not respond to topical therapy and does not improve to grade 1 severity within 2 weeks of starting therapy OR requires systemic treatment
- Recurrent grade 2 pneumonitis
- Symptomatic heart failure associated  $\geq 10\%$  reduction in LVEF
- Grade 3 uveitis, pneumonitis, bronchospasm, diarrhea, colitis, neurologic toxicity, hypersensitivity reaction, or infusion reaction
- Any grade 3 non-skin, drug-related AE lasting  $>7$  days, with the following exceptions:
  - Grade 3 endocrinopathies adequately controlled with only physiologic hormone replacement do not require discontinuation
  - Grade 3 laboratory abnormalities do not require treatment discontinuation except:
    - Grade 3 thrombocytopenia  $>7$  days OR that is associated with bleeding requires discontinuation
    - Any liver function test (LFT) abnormality that meets the following criteria require discontinuation:
      - Total bilirubin  $>3 \times$  ULN
      - Concurrent AST or ALT  $>3 \times$  ULN **and** total bilirubin  $>2 \times$  ULN
      - In participants with liver metastasis with baseline grade 2 elevation of AST or ALT, hepatitis with AST or ALT increases  $\geq 50\%$  and lasts  $\geq 1$  week
- Any grade 4 AE or laboratory abnormality, except for the following events which do not require discontinuation:
  - Grade 4 amylase or lipase abnormalities that are not associated with symptoms or clinical manifestations, or radiographic signs of pancreatitis. It is recommended to consult with the IND Sponsor for grade 4 amylase or lipase abnormalities.
  - Isolated grade 4 electrolyte imbalances/abnormalities that are not associated with clinical sequelae and are corrected with supplementation/appropriate management within 72 hours of their onset.
  - Grade 4 lymphopenia and leukopenia.
  - Grade 4 treatment-related endocrinopathy adverse events, such as adrenal insufficiency, ACTH deficiency, hyper- or hypothyroidism, or glucose intolerance, which resolve or are adequately controlled with physiologic hormone replacement (corticosteroids, thyroid hormones) or glucose-controlling agents, respectively, may not require discontinuation after discussion with and approval from the IND Sponsor.
- Any grade 5 adverse event
- Any dosing interruption lasting  $>6$  weeks with the following exceptions:
  - Dosing interruptions to allow for prolonged steroid tapers to manage drug-related adverse events are allowed.
  - Dosing interruptions  $>6$  weeks that occur for non-drug-related reasons may be allowed if approved by the Principal Investigator.
  - Prior to re-initiating treatment in a subject with a dosing interruption lasting  $>6$  weeks, the Principal Investigator must be consulted.

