### 1.2 Secondary Objectives

- 1.2.1 To assess the safety and tolerability of combination of atezolizumab and CDX-1127 (varlilumab) with or without cobimetinib in patients with unresectable, pre-treated biliary cancers.
- 1.2.2 To assess overall survival (OS) of patients with unresectable, pre-treated biliary cancers treated with the combination of atezolizumab and CDX-1127 (varlilumab) with or without cobimetinib.
- 1.2.3 To determine the effect of combination atezolizumab and CDX-1127 (varlilumab) +/- cobimetinib on T cell subpopulations systemically and intratumorally.

[REDACTED]

1.3.1 [REDACTED]

1.3.2 [REDACTED]

1.3.3 [REDACTED]

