***Adverse Events of Interest:***

**Hemorrhage:** Hemorrhage, including major hemorrhages defined (symptomatic bleeding in a critical area or organ), can occur with cobimetinib. Events observed included cerebral hemorrhage, GI hemorrhage, reproductive tract hemorrhage, and hematuria.

In randomized phase 3 trial of cobimetinib + vemurafenib vs. vemurafenib-placebo, hemorrhagic events were 13.0% with cobimetinib + vemurafenib vs. 7.3% with vemurafenib. Grade 3 to 4 hemorrhage occurred in 1.2% vs. 0.8% of patients. Increased hemorrhage was seen in several sites: cerebral hemorrhage (0.8% vs. 0), gastrointestinal tract hemorrhage (3.6% vs. 1.2%), reproductive system hemorrhage (2.0% vs. 0.4%), and hematuria (2.4% vs. 0.8%).

Caution should be used in patients with additional risk factors for bleeding, such as brain metastases, and/or in patients that use concomitant medications that increase the risk of bleeding (including antiplatelet or anticoagulant therapy).

**Cardiomyopathy:** Cardiomyopathy, defined as symptomatic and asymptomatic decline in left ventricular ejection fraction (LVEF), can occur with cobimetinib. The safety of cobimetinib has not been established in patients with a baseline LVEF that is either below institutional lower limit of normal (LLN) or below 50%. In randomized phase 3 trial of cobimetinib + vemurafenib vs. vemurafenib + placebo, patients were assessed for LVEF by echocardiograms or multiple-gated acquisition (MUGA) at baseline, Week 5, Week 17, Week 29, Week 43, and then every 4 to 6 months thereafter while receiving treatment.

Grade 2 or 3 decrease in LVEF occurred in 26% vs. 19% of patients receiving the combination vs. vemurafenib. The median time to first onset of LVEF decrease was 4 months (range: 23 days to 13 months). Two patients on the combination arm (0.8%) were symptomatic

Of the patients with decreased LVEF, 22% had dose interruption and/or reduction and 14%

required permanent discontinuation. Decreased LVEF resolved to above the LLN or within 10% of baseline in 62% of patients receiving cobimetinib with a median time to resolution of 3 months (range: 4 days to 12 months).

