| Hepatotoxicity | Right upper-quadrant abdominal pain and/or unexplained nausea or vomiting | 
Risk of immune-mediated hepatitis. LFTs should be performed immediately, and LFTs should be reviewed before administration of the next dose of study drug. For patients with elevated LFTs, concurrent medication, viral hepatitis, and toxic or neoplastic etiologies should be considered and addressed, as appropriate.
 
Symptoms of abdominal pain associated with elevations of amylase and lipase, suggestive of pancreatitis, have been associated with the administration of atezolizumab & CDX-1127 (varlilumab). The differential diagnosis of acute abdominal pain should also include pancreatitis, as described below.
 | 
Risk of immune-mediated hepatitis. LFTs should be performed immediately, and LFTs should be reviewed before administration of the next dose of study drug. For patients with elevated LFTs, concurrent medication, viral hepatitis, and toxic or neoplastic etiologies should be considered and addressed, as appropriate.
 
Symptoms of abdominal pain associated with elevations of amylase and lipase, suggestive of pancreatitis, have been associated with the administration of atezolizumab & CDX-1127 (varlilumab). The differential diagnosis of acute abdominal pain should also include pancreatitis, as described below.
 |
|                | Hepatic event, general guidance   | Consider possible tumor-related etiology, and consider earlier restaging imaging to inform clinical decision making (e.g. steroid initiation)  | Consider possible tumor-related etiology, and consider earlier restaging imaging to inform clinical management (e.g. steroid initiation)   |
|                | Grade 1 hepatic event   | Continue atezolizumab & CDX-1127   | Continue atezolizumab & CDX-1127   |

|  |   |  |  |
|--|---|--|--|
|  |   | (varlilumab).

Monitor LFTs weekly until values resolve to within baseline values.   | (varlilumab) and cobimetinib.

Monitor LFTs weekly until values resolve to within normal limits. |

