|   | H: Clinical hematology: CBC with differential ANC, ALC, AEC, and platelet count. Labs may be collected within a window of up to 7 days prior to Cycle 1 Day 1 dosing and up to 3 days prior to all other dosing days. Initial screening bloodwork does not need to be repeated if performed within 7 days of CD1.  |                     |        |        |         |       |        |                    |        |       |  |
|   | I: Serum Chemistry should include Glucose, Calcium, Sodium, Potassium, $\text{CO}_2$ , Chloride, BUN, Creatinine, Alkaline phosphatase (ALT), Aspartate amino transferase (AST), Bilirubin, Albumin, GGT, Total Protein, and LDH. For patients on Arm A (i.e. receiving cobimetinib), also include Phosphorus and Magnesium. Labs may be collected within a window of up to 7 days prior to Cycle 1 dosing and up to 3 days prior to all other dosing days. Initial screening bloodwork does not need to be repeated if performed within 7 days of CD1.  |                     |        |        |         |       |        |                    |        |       |  |
|   | J: Baseline thyroid testing should be done only in patients with a known history of thyroid dysfunction and/or if there is a clinical concern for thyroid dysfunction at the time of study screening. Free T3/T4 should be checked reflexively if fTSH is abnormal. Subsequent labs during treatment may be collected within a window of up to 3 days prior to dosing days.  |                     |        |        |         |       |        |                    |        |       |  |
|   | K: Serum or urine pregnancy (women of childbearing potential only) is required at baseline. For women with a mildly elevated B-HCG who in the opinion of the investigator are not pregnant, a vaginal ultrasound must be obtained to confirm that the participant is not pregnant in order to enroll on this study. Pregnancy tests during treatment as clinically indicated.  |                     |        |        |         |       |        |                    |        |       |  |

| Visit window d  | Baseline                           |                      | Cycle 1 |        |        | Cycle 2 |       |        | Cycle 3 and beyond |        |       | Progression/
End of
Treatment e |        |        |
|--|------------------------------------|----------------------|---------|--------|--------|---------|-------|--------|--------------------|--------|-------|--|--------|--------|

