| R: D1 of Cycles 1-6, 9, 12; pharmacokinetic and immunogenicity: pharmacokinetic blood draws will be performed pre-infusion and 30 minutes after the end of infusion of CDX-1127 (varilumab), which will be administered after atezolizumab and D15 of Cycle 1 and 2. See Section 5.1 for more details.   |                                    |                      |         |        |        |         |       |        |                    |        |       |  |        |        |
| S: End of Treatment evaluations will be completed no more than 30 days after the last dose of all study drugs and prior to start of next line systemic therapy.  |                                    |                      |         |        |        |         |       |        |                    |        |       |  |        |        |
| T: Patients receiving cobimetinib ( study arm A only ). Labs during treatment may be collected within a window of up to 3 days prior to dosing days.  |                                    |                      |         |        |        |         |       |        |                    |        |       |  |        |        |
| U: Evaluation of LV function by either echocardiogram (ECHO) or multiple-gated acquisition (MUGA) at baseline ( all patients ), 1 month after first dose ( study arm A only ), then every 3 months while on cobimetinib (visit window $+/-7$ days); ( study arm A only ).   |                                    |                      |         |        |        |         |       |        |                    |        |       |  |        |        |

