| V: Ophthalmologic examination at baseline ( all patients , within 4 weeks prior to randomization ), then every 2 months for 1 year ( study arm A only ), then every 6 months while on cobimetinib (visit window $+/-14$ days); ( study arm A only ). Eye exam should include retinal exam, slit lamp exam, and visual fields (preferably Goldmann Visual Field if available) for evidence of retinal pathology and other abnormalities. Alternatives to Goldmann Visual field tests such as Humphrey and Octopus visual field tests/machines are acceptable. Alternatives to checking visual acuity with Landolt chart such as ETDRS and documentation of Snellen equivalent are acceptable.   |                                    |                      |         |        |        |         |       |        |                    |        |       |  |        |        |
| W: Adverse events will be assessed at least 30 days after the last dose of either study agent. For patients removed due to unacceptable toxicity, they will be followed until resolution of the adverse event.   |                                    |                      |         |        |        |         |       |        |                    |        |       |  |        |        |
| X: End of Cycle 3 only (including up to prior to starting treatment on C4D1).  |                                    |                      |         |        |        |         |       |        |                    |        |       |  |        |        |
| Y: Before the on-study biopsy.   |                                    |                      |         |        |        |         |       |        |                    |        |       |  |        |        |
| Z: Patients receiving cobimetinib ( study arm A only ). EKG will be performed after randomization but before C1D1, at C1D15, monthly during the first 3 months, and then every 3 months thereafter or more often as clinically indicated.   |                                    |                      |         |        |        |         |       |        |                    |        |       |  |        |        |

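### Arm A alone has scheduled cardiac, eye, ECG and extra laboratory tests on treatment, so the planned AE-rate and time-to-first-toxicity models, if read between arms, mix drug effect with testing effect

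*Combined protocol and SAP*

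**What the plan says.** Safety is a secondary objective covering both regimens (Section 1.2): "To assess the safety and tolerability of combination of atezolizumab and CDX-1127 (varlilumab) with or without cobimetinib". Section 9.5.1 gives the model-based part of the analysis: "Negative binomial regression and Cox proportional hazards models will be used to assess the rate of AE and time to first toxicity, respectively". It names no arm covariate, no event set for the models and no rule for events found by tests that only one arm receives. It does allow an analysis of a specific safety parameter, such as laboratory shifts, to require a baseline value and at least one value after dosing. That condition is optional and is not applied to the AE rate or to time to first toxicity.

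I use Arm A for the triplet, as Section 6.1 and the calendar do (the CD8 analysis in Section 9.4 uses the letters the other way round). The footnotes to the Section 11 calendar set these schedules:

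- **ECHO/MUGA (U):** all patients at baseline. Then Arm A only, at 1 month and "then every 3 months while on cobimetinib".
- **Eye examination (V):** all patients at baseline. Then Arm A only, every 2 months for a year and "then every 6 months while on cobimetinib". Otherwise an examination is prompted by ocular symptoms (M).
- **ECG (Z, Arm A only):** "EKG will be performed after randomization but before C1D1, at C1D15, monthly during the first 3 months", then every 3 months.
- **Chemistry (I):** "For patients on Arm A (i.e. receiving cobimetinib), also include Phosphorus and Magnesium".
- **CPK:** all patients at baseline. The footnote marker in this row is unreadable in the extracted text. Footnote T, the Arm-A-only note on laboratory tests during treatment, is the one that fits, so Arm-A-only CPK is an inference.

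**The concern.** An asymptomatic fall in LVEF, an early retinal change, an ECG abnormality or a low phosphate becomes an adverse event only if someone looks for it. On treatment, Arm A is looked at on a timetable and Arm B when something prompts it. If such events arise at the same rate in both arms, more of them will still be recorded in Arm A.

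An AE rate ratio or a hazard ratio for first toxicity between the arms would then estimate two things together: what cobimetinib does and what the extra testing finds. The testing part can only push against the triplet. Detection also changes within Arm A, because the ECHO and eye schedules stop with cobimetinib while Section 7.2.2 allows the two antibodies to continue. At stake is what the trial can conclude about the toxicity that cobimetinib adds to the doublet.

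**Working it through.** The documents give no sample size, power or expected rate for the AE models, so there is no planned figure to reproduce. The check asks how large a spurious difference could be when the arms are truly equal.

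**Inputs from the documents**

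- 32 patients per arm (Section 9.2).
- LVEF in the phase 3 melanoma trial, assessed on a common schedule (Section 2.2.2.2.3): "Grade 2 or 3 decrease in LVEF occurred in 26% vs. 19% of patients receiving the combination vs. vemurafenib". Symptomatic on the combination: 0.8% of patients, so 0.8/26, about 3% of those with a fall.
- CPK elevation in the same trial: 32.4% with cobimetinib and 8.1% without. Most elevations on cobimetinib monotherapy were without symptoms.
- Any-grade AE on atezolizumab alone: 619 of 629, or 98.4% (Section 2.2.1.3.2).

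**Assumption.** The rates without cobimetinib, 19% and 8.1%, stand in for the background in both arms here, and all of these events are found by scheduled test only. At 32 per arm that is 32 × 0.19 = 6.1 and 32 × 0.081 = 2.6 patients, together 8.7. Per patient, m = 0.19 + 0.081 = 0.271 test-only events.

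**AE rate.** With λ events per patient detectable in both arms, the rate ratio is (λ + m)/λ:

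| λ | Rate ratio |
|---|---|
| 0.5 | 1.54 |
| 1 | 1.27 |
| 2 | 1.14 |
| 5 | 1.05 |
| 10 | 1.03 |

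**Time to first toxicity.** With constant hazards, cumulative incidence pc of clinically detected toxicity and pt of test-only toxicity, HR = [ln(1 − pc) + ln(1 − pt)] / ln(1 − pc). Example: pc = 0.20 and pt = 0.10 give (0.223 + 0.105)/0.223 = 1.47. The 5%, 10% and 25% values of pt are assumed, not taken from the documents.

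| pc | pt = 5% | pt = 10% | pt = 25% |
|---|---|---|---|
| 20% | 1.23 | 1.47 | 2.29 |
| 50% | 1.07 | 1.15 | 1.42 |
| 80% | 1.03 | 1.07 | 1.18 |
| 98.4% | 1.01 | 1.03 | 1.07 |

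**Chance of a false finding.** I simulated exponential times with 32 per arm, no true difference and 10,000 runs, using a two-sided 5% Wald test of the log rate ratio of first events as a stand-in for the Cox test. The probability of a significant result against the triplet was:

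- about 0.02 with equal testing;
- 0.09 and 0.40 at pc = 20% with pt = 10% and 25%;
- 0.06 and 0.18 at pc = 50% with the same pt.

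Restricting the models to events ascertained alike in both arms sets m and pt to zero. The spurious ratios return to 1.00 and the error rate to about 0.02.

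**The case against.** Section 9.5.1 does not say that the models compare arms. Where the protocol intends a comparison it says so, as for PFS and CD8 density, and the safety stopping rule works within each arm. This stands as a limit: the problem arises only when the models are read between arms. But a 1:1 trial of a doublet with or without cobimetinib invites that reading, and the plan does not exclude it.

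A reader might infer a large artefact from single event types. If Arm B recorded no LVEF events, 8 of 32 against 0 of 32 gives a Fisher p of 0.005, where 8 against 6 gives 0.76. For CPK, 10 against 0 gives 0.0009, where 10 against 3 gives 0.06. The documents do not support that inference. No such test is planned, and zero is the extreme case for Arm B. The background rates come from melanoma patients on vemurafenib, a drug not used here. Treatment there was probably longer: median PFS was 12.3 and 7.2 months, against 7 and 3.5 assumed in Section 9.2. Median onset of LVEF decrease was 4 months, so fewer events may be found here. The phase 3 trial also had no high-grade CPK elevation without cobimetinib, and the 19% is not split by grade. For a grade 3 or higher outcome the test-only share may therefore be at the low end of the assumed range, or below it.

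A further objection is that removing test-detected events hides real harm, since CPK elevation was 32.4% against 8.1% with both arms reported. That is right, and it is why the restricted model should sit beside the all-AE model rather than replace it.

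The optional post-dose measurement condition helps parameter-specific tables only.

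**Conclusion.** The point holds in a limited form. Five types of on-treatment test, and by inference CPK, are scheduled in Arm A only, and the planned AE models make no allowance for it. Read between arms, they confound drug effect with testing effect, against the triplet. A true excess from cobimetinib is also expected, and the planned models cannot separate the two.

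The size is unknown. For any-grade events it is small: rate ratio 1.03 to 1.05 at 10 to 5 events per patient, hazard ratio 1.01 to 1.07 if the 98.4% incidence carries over. It becomes material for less frequent outcomes, such as related grade 3 or higher events: hazard ratio 1.2 to 2.3 at 20% clinical incidence with 5% to 25% test-only incidence. These ranges are assumptions, with constant hazards and no true difference.

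One separate inconsistency adds little to this. In the Grade 1 hepatic row of Section 7.3, the triplet column reads "Monitor LFTs weekly until values resolve to within normal limits", while the doublet column ends monitoring at baseline values. Monitoring is weekly in both columns and starts after an event is already known. The two end-points should be reconciled.

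**What to change.** In Section 9.5.1, before outcome data are seen:

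1. Keep the all-AE negative binomial and Cox models, say whether arm is a covariate, and state that any between-arm contrast from them includes unequal ascertainment.
2. Add pre-specified between-arm negative binomial and Cox models restricted to events ascertainable on the same schedule in both arms. Exclude, by a list of AE terms fixed in advance, asymptomatic LVEF, retinal, ECG, CPK, phosphate and magnesium findings. Selection by term is needed because Section 10.2 describes AEs by term, grade and attribution, not by how they were detected.
3. Report the excluded findings descriptively within Arm A, per test performed.

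The cost is analysis wording and a few more tables, assuming that the tests performed are recorded. No monitoring schedule changes. The downside is that the restricted models omit some real cobimetinib toxicity, and a term list may remove some symptomatic events too. The two sets of models must therefore be read together.

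Separately, reconcile the two columns of the Grade 1 hepatic row in Section 7.3.
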